6.3.1.1 Primary Endpoints

Safety: Incidence of AEs and SAEs from commencement of IMP administration through to the time of the last study visit will be evaluated. Vital signs, laboratory measures, physical exam results (neurological, ophthalmologic, and general) urine output history, will also be evaluated from screening/baseline through the end of the study.

Tolerability: Tolerability will be assessed based on caregiver reports and the caregiver diary, required dosing adjustments or discontinuations, dosing compliance and AEs related to participant experience.

Pharmacokinetic:

NNZ-2591 PK concentrations will be listed by participant and time point for each dose level with actual time they were acquired. The concentrations will be summarized by time, dose level and age group. For the concentrations measured at trough points dose relationship will be examined statistically with age group and/or body weight of participant as covariate.

Overall exposure parameters for NNZ-2591 such as C_{max} and AUC_{tau} may be derived by sparse non-compartmental analysis (NCA). Additionally, PK concentrations of NNZ-2591 measured in pediatric

participants will be used to refine a population PK model developed from adult NNZ-2591 PK data and extrapolated to pediatric population. After refinement, complete profiles for each participant will be simulated using a range of variability of model parameters and individual covariate effects. A standard NCA approach will be used for simulated profiles to calculate parameters C_{max} , AUC_{tau} , etc. for characterization of NNZ-2591 exposure in pediatric participants.

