7.2.2 Dose Escalation Review by the DSMC

Data from two weeks of dosing at each dose in the dose escalation will be reviewed by the DSMC before participants are allowed to be administered the next highest dose. Participants will stay on their current dose until the DSMC has reviewed the data and approved the participants to escalate to the next dose.

After eligibility is confirmed, the participant will be administered NNZ-2591 IMP open label at a starting dose of 4 mg/kg BID for a total of approximately 3 weeks. After 2 weeks of dosing at 4 mg/kg BID, the DSMC will review the safety data. The participant will remain on the starting dose during the DSMC review. If the DSMC determines that tolerability and safety during the 2-week dosing period are acceptable, the participant will escalate to the next dose of 8 mg/kg BID and be dosed for a total of approximately 3 additional weeks at that dose. After 2 weeks of dosing at 8 mg/kg BID, the DSMC will review the safety data. If the DSMC determines that tolerability and safety during the 2-week dosing period on 8 mg/kg BID are acceptable, the participant will then escalate to the target dose of 12 mg/kg BID and be dosed for 2 weeks. After 2 weeks of dosing at 12 mg/kg BID, the DSMC will review the safety data to determine if the participant can continue dosing at 12 mg/kg BID for the remainder of the 13 weeks.

The DSMC will determine if dose escalation can proceed based on pre-specified stopping rules summarized for individual participants in Section 9.4.5. Note that early cessation of IMP treatment does not necessarily mean the participant is withdrawn from the study. With any early cessation, all evaluations and tests scheduled during the study must be conducted if possible.

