The site will inform the caregiver of the up-titration decisions as soon as possible after the site has received the official notification of the DSMC decision. The site will verify with the caregiver that instructions to up-titrate to 8 mg/kg BID have been followed at the Week 4 visit (Visit 7), and will verify with the caregiver that instructions to up-titrate to 12 mg/kg BID have been followed at the Week 7 visit (Visit 10). If the DSMC has not yet approved the participant to escalate to the next dose by the time of the relevant visit, the site should contact the caregiver within 24 hours of receiving the decision from the DSMC. If the participant is not approved to titrate to the next dose, the site will contact the caregiver to discuss appropriate follow-up as is clinically indicated. At each visit, the clinician or nurse should check the dose when reviewing the caregiver diary.

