- Attention Deficit Disorder will be derived from the PTHS diagnosis page of the CRF. If "Attention Deficit Disorder" is checked under "confirmation of psychiatric co-morbidities", the subject is considered as having the disorder.
- Obsessive-compulsive Disorder will be derived from PTHS diagnosis page of the CRF. If "Obsessive-compulsive disorder" is checked under "confirmation of psychiatric co-morbidities", the subject is considered as having the disorder.
- There will be three age group definitions use for the analysis and applied to all analyses requiring an analysis by age group:
  - Enrollment Age Group
    - 13 to 17 years old
    - 8 to 12 years old
    - 3 to 7 years old
  - Child/Adolescent Age Group
    - 13 to 17 years old
    - 3 to 12 years old
  - Divided Age Group
    - 16 to 17 years old
    - 13 to 15 years old
    - 8 to 12 years old
    - 3 to 7 years old
- Dose modification is defined as dose increased, dose reduced, or dose interrupted responses for the action taken with study treatment on the AE CRF.
- TEAEs are defined as those adverse events that occurred after the administration of first dose of study drug.
- Improvement in the Top 3 concerns will be derived as a decrease in severity (change from baseline < 0). This is calculated for the average score and for individual concerns by the symptom domains as defined in Section 9.2.8.

- The baseline seizure frequency will be determined based on the number of seizures recorded in the diary during the 4–6-week screening period. The baseline monthly seizure frequency will be derived by dividing the total number of seizures during the screening/baseline period by the screening/baseline duration in months (screening/baseline duration divided by 30.4375). During the treatment period (Visits 4 6), the seizure frequency will be derived by summing the number of seizures recorded in the diary over treatment. The monthly seizure frequency will be derived by dividing the total number of seizures during the treatment duration in months (screening/baseline duration divided by 30.4375).

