### 7.1 Dosing Summary

Treatment duration and study duration will be derived as stated in Section 5.3 and summarized using descriptive statistics.

The maximum dose level (8 mg/kg BID, or 12 mg/kg BID) reached by each subject will be summarized according to the Dosing Compliance CRF as a frequency distribution. The number of missed doses as defined in Section 5.3 will be summarized. The number of missed doses will only be defined prior to discontinuation of treatment.

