### 7.2 Adverse Events

Adverse events will be recorded from the time of first dose of IMP until Follow-up (Visit 17). Adverse events summaries will only consider treatment emergent adverse events (TEAEs). TEAEs are defined as those adverse events that occurred after the administration of the first dose of study drug. If it cannot be determined whether the adverse event is treatment emergent due to missing or incomplete (partial) onset dates, dates will be imputed for the purposes of determining treatment emergence as described in Section 5.2.1.

Verbatim terms entered into the clinical database via the EDC system will be mapped to preferred terms and system organ classes using version 24.0 of MedDRA.

Summaries that are displayed by SOC and PT will be ordered by descending order of incidence of SOC and PT within each SOC. Adverse event summaries of the following types will be presented for the Safety Population:

- Overall summary of the TEAEs which contain an overview of each item below.
- Subject count and incidence rate of TEAEs and total number of unique TEAEs by MedDRA system organ class and preferred term.
- Subject count and incidence rate of TEAEs by MedDRA preferred term and greatest intensity. Intensity is defined by three categories: "Mild", "Moderate", and "Severe." At each level of subject summarization, a subject is classified according to the greatest intensity if the subject reported one or more events. Adverse events with missing intensity will be considered severe for this summary.
- Subject count and incidence rate of TEAEs by MedDRA preferred term and closest relationship to study drug (Related/Not Related). At each level of subject summarization, a subject is classified according to the closest relationship if the subject reported one or more events. Adverse events with missing relationship will be considered related for this summary.
- Subject count and incidence rate of Serious TEAEs by MedDRA SOC and PT.
- Subject count and incidence rate of TEAEs by dose level, SOC, and PT.
- Subject count and incidence rate of related TEAEs by dose level, SOC, and PT.
- Subject count and incidence rate of TEAEs leading to withdrawal of study medication by MedDRA SOC and PT.
- Subject count and incidence rate of TEAEs leading to dose modification (defined as dose increased, dose reduced, or dose interrupted on the CRF) by MedDRA SOC and PT.
- Subject count and incidence of TEAEs with an outcome of death by MedDRA SOC and PT.

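### The table of TEAEs leading to dose modification pools increases with reductions and interruptions and cannot show an escalation withheld or delayed for an AE; the maximum-dose summary covers this only partly.

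*SAP*

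**What the plan says.** The protocol's tolerability endpoint is one of the primary endpoints. It rests on caregiver reports and the diary, and on "required dosing adjustments or discontinuations, dosing compliance and AEs related to participant experience" (Protocol 6.3.1.1). SAP 7 lists similar components.

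Dose modification is defined in SAP 5.3: "Dose modification is defined as dose increased, dose reduced, or dose interrupted responses for the action taken with study treatment on the AE CRF". SAP 7.2 then plans "Subject count and incidence rate of TEAEs leading to dose modification (defined as dose increased, dose reduced, or dose interrupted on the CRF"), by system organ class and preferred term. The SAP addendum alters only the missed-doses item in Section 5.3, so this definition stands.

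Two companion outputs matter. SAP 7.2 also plans "Subject count and incidence rate of TEAEs leading to withdrawal of study medication by MedDRA SOC and PT". SAP 7.1 adds: "The maximum dose level (8 mg/kg BID, or 12 mg/kg BID) reached by each subject will be summarized according to the Dosing Compliance CRF".

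On titration, Protocol 7.2.2 says: "Participants will stay on their current dose until the DSMC has reviewed the data and approved the participants to escalate to the next dose". It also provides for refusal: "If the participant is not approved to titrate to the next dose, the site will contact the caregiver". Protocol 7.2.1 separately allows a child who is not tolerating a dose during up-titration to go down one level, requires an attempt to go back up, and otherwise keeps the child on the highest tolerated dose.

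**The concern.** The definition fits a trial in which every child starts on the full dose, where intolerance shows as a reduction, an interruption or a stop. Here the schedule starts at 4 mg/kg BID and plans two increases. An AE can therefore limit dosing in another way: the next step does not happen, or happens late. None of the three listed actions describes that.

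The inclusion of dose increases has the opposite problem. Going up is the planned course, and going back up after a down-titration is something the Investigator must attempt. An increase is not in itself a sign of poor tolerability, so a count that pools it with reductions and interruptions cannot be read as a count of intolerance.

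At stake is a descriptive table that feeds a primary endpoint in a small trial. A reader who takes it as the number of children whose dosing was limited by AEs short of withdrawal could get a figure too low on one account and too high on the other.

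**Working it through.** The documents give no figure on this point, so there is none to reproduce. The check sets each possible consequence of an AE against the planned outputs, taking that consequence as the only one the AE had.

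| Consequence of the AE | Dose-modification table (SAP 7.2) | Other planned summary |
|---|---|---|
| Dose reduced | Counted | Maximum dose shows the highest level reached |
| Dose interrupted | Counted | None specific |
| Drug withdrawn | Not in this table | Own table in SAP 7.2 |
| Dose increased, recorded as action taken | Counted with reductions and interruptions | None specific |
| Step withheld, child stays at 8 mg/kg BID | Not counted | Seen in SAP 7.1 as 8 mg/kg BID, no AE link |
| Step withheld, child stays at 4 mg/kg BID | Not counted | No named level in SAP 7.1 |
| Step delayed for the AE, then made | Not counted | SAP 7.1 looks the same as for an undelayed child |

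The last three rows are the gap. TEAEs by dose level (SAP 7.2) do not close it, because they show the dose at which an event occurred and not whether it held back the next step. The gap is widest at the starting dose: down-titration goes to the next lower scheduled level, and Protocol Table 4 has none below 4 mg/kg BID. A child simply held there has no reduction to record within that schedule.

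**Scale.** The planned sample is N = 10 to 20 (Protocol 7.1), so one child is 1/10 = 10% or 1/20 = 5%. The documents give no rate of withheld escalation. For an assumed rate p, the chance of at least one such child is 1 − (1 − p)^N:

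| Assumed p | N = 10 | N = 20 |
|---|---|---|
| 5% | 1 − 0.95^10 = 40% | 1 − 0.95^20 = 64% |
| 10% | 1 − 0.90^10 = 65% | 1 − 0.90^20 = 88% |
| 20% | 1 − 0.80^10 = 89% | 1 − 0.80^20 = 99% |

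**Illustration, assumed numbers only.** Suppose 16 children are treated, 2 are held below target because of AEs, and no child has a reduction, an interruption or an increase recorded as the action taken for an AE. The dose-modification table reads 0/16 (0%). The proportion with dosing limited by an AE is 2/16 = 12.5%, with an exact (Clopper-Pearson) 95% interval of 1.6% to 38%. If both were held at 8 mg/kg BID, SAP 7.1 would show 2/16 at that level without a reason. If both were held at 4 mg/kg BID, they would have no named row.

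**The case against.** The other side has a good deal of substance.

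- **Most AE-driven dosing changes are tabulated.** The protocol's stated route for a dose not tolerated during up-titration is to go down a level, which counts as a reduction. Interruptions are in the same table and withdrawals have their own. A reader might infer that the table misses the main tolerability failure of the trial. The documents do not support that, because nothing in them ranks withheld escalation above these other outcomes.
- **A withheld step is not wholly lost.** SAP 7.1 shows a child whose maximum was 8 mg/kg BID, tolerability rests on several sources, and CRF data are to be listed by subject as appropriate (SAP 10). This stands, but leaves the three limits in SAP 7.1: no 4 mg/kg BID level, no AE link and no delays.
- **Scheduled increases are not counted automatically.** An increase enters only if it is recorded as the action taken for an AE. A reader might multiply two planned steps by the number of children and treat the product as miscounts. That product counts opportunities, not errors. The AE CRF and its instructions are not in the documents, so coding practice is unknown.
- **The titration is not forced.** A reader might describe it so, but each step is gated by the DSMC and a child may continue on the highest tolerated dose.
- **Delay needs a definition.** Children already wait on their current dose during DSMC review, expected to take one week, so a late decision must be told apart from a delay caused by an AE. This objection is correct and shapes the fix.

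**Conclusion.** The point holds as a reporting gap. By its own definition, the dose-modification table cannot show an escalation withheld or delayed because of an AE, and it mixes increases with signs of intolerance. SAP 7.1 fills part of the gap.

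Each child whose only consequence was a withheld or delayed step contributes 0 to the table where 5% to 10% of the sample would be at issue. How many such children there would be cannot be derived from the documents. The probabilities and the 2/16 example rest on assumed rates and show scale only. The conclusion also assumes that the AE CRF's action-taken field is used as SAP 5.3 describes, with no separate response for a withheld step.

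No efficacy result depends on this, and it does not question any dosing or titration rule. It is a cheap improvement that makes the primary tolerability output more complete.

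**What to change.** 1. In SAP 5.3 and 7.2, report dose increased separately from dose reduced and dose interrupted.
2. In the same sections, add a count and a by-subject listing of children whose scheduled escalation was withheld or delayed because of an AE. Take these from the DSMC or Investigator titration decisions and the dosing records. State how a delay is identified, and keep it distinct from waiting time due only to DSMC review.
3. In SAP 7.1, list 4 mg/kg BID among the maximum dose levels.

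The first and third changes are SAP wording. The second also needs data review to link titration decisions to individual AEs, for at most about 20 children. The documents do not show that the reason for a withheld step is held in the analysis database, so some attribution may be a matter of judgement and should be settled before database lock. SAP 5 treats any analysis added after lock as exploratory.

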### 6 Subject Information

### 6.1 Subject Disposition

Information regarding subject disposition will be summarized for all subjects by age groups as defined in Section 5.3 and overall.

Summaries will include: number of subjects enrolled, number of subjects who screen failed, number of subjects in the ITT, Safety, and mITT populations, number of subjects

who complete the study, and number of subjects who discontinue the study early. For those who discontinue early, the primary reason for discontinuation will be summarized. The primary reason for discontinuation from the CRF will be mapped to the Completion/Reason for Non-Completion SDTM Terminology for presentation in the table. A data listing by subject will also be generated.

### 6.2 **Protocol Deviations**

Protocol deviations will be collected throughout the duration of the study. Protocol deviations will be assigned a sponsor-defined category type. Each deviation will be defined as important or not important. In addition, a by-subject listing of all protocol deviations (important and not important) will be produced.

### 6.3 Demographic and Baseline Characteristics

Demographics variables will include: age, age groups, sex, ethnicity, race, height at baseline, weight at baseline, and BMI at baseline. Age and BMI will be derived as specified in Section 5.3.

Baseline characteristics will include: PTHS Variant Types (as recorded on the CRF), history of developmental regression, Autism Mental Status Exam, seizure types at screening (as recorded on the CRF), presence of co-morbid psychiatric disorders (e.g. Autism Spectrum Disorder (ASD), bipolar disorders, attention deficit disorder, obsessive-compulsive disorder), and Stanford-Binet Intelligence Scales version 5 (SB5) NVIQ standard and z-deviation score or the Bayley Scales of Infant Development – Version 4 (BSID-4) NVDQ for subjects who cannot basal on the SB5 or for whom the SB5 is not developmentally appropriate. If the SB5 was attempted but the child was unable to basal on the assessment, the BSID-4 should be administered. If partial scores for the SB5 are entered in the EDC in addition to the BSID-4, only the BSID-4 scores will be summarized. If the child has complete sets of scores on the SB5 and the BSID-4, the scores for the assessment that was captured at both Screening and EOT will be summarized. If a participant has a complete set of scores for the SB5 and BSID-4 at both Screening and EOT, these cases will be adjudicated by the Sponsor before database lock.

Demographics and baseline characteristics will be summarized for all analysis populations (ITT Population, Safety Population, mITT Population).

Subjects will be evaluated for PTHS at the Screening Visit. The diagnosis and genotype will be documented. PTHS genotypes will be summarized and listed by subject.

History of developmental regression will be determined from the question as reported on the PTHS diagnosis page in the CRF: "Has the child undergone a regression of skills in

the past?" If coded as "yes" the subject is considered as having had a past developmental regression.

The Autism Mental Status Exam (AMSE) will be performed at the Screening Visit. The AMSE is an 8-item observational assessment used to document communicative and behavioral functioning in subjects with ASD. Each question is scored as 0, 1, or 2. The range of the AMSE score is 0 - 14. Higher scores indicate greater severity of autistic symptoms. A question assessing overall impairment is also completed evaluated on a 4-point scale: No impairment, Mild, Moderate and Severe.

The scoring algorithm is below:

- Question 1-4, Eye Contact, Interest in Others, Pointing Skills, Language: each response is assigned a score of 0, 1, or 2 in the order they appear on the CRF.
- Question 5 Pragmatics of Language: Not Impaired or Not Applicable=0, Reported=1, Observed=2
- Question 6 Repetitive Behaviors/Stereotypy: None=0, Insists on routines=1, any other response=2
- Question 7-8 Unusual or Encompassing Preoccupations, Unusual Sensitivities: None=0, Reported=1, Observed=2

The AMSE score is the sum of the individual question scores above and will only be calculated if no items are missing. The AMSE score and the overall impairment will be summarized.

Seizure type ("Clinical Type" in Seizures and Spells Log form on the CRF recorded at Baseline) and characteristics of seizures ("Description in Seizure Types at Screening" form on the CRF: change in awareness, loss of urine or bowel control, loss of ability to communicate, automatic repeated movements, rhythmic jerking muscle, falls if standing or sitting, head drops, warning before seizure occurred, common triggers, muscle stiffness, muscle twitch, other) are recorded at the Screening Visit for subjects. These descriptive characteristics will be summarized using frequencies and percentages.

The presence of other co-morbid psychiatric disorders will be recorded on the PTHS Diagnosis page of the CRF. If the disorder is checked on the CRF, it will be considered as present in the subject.

## 6.4 Medical History

Medical history will be coded using Medical Dictionary for Regulatory Activities (MedDRA) version 24.0 and listed by System Organ Class (SOC), Preferred Term (PT), and verbatim term. A complete medical history will be recorded at all Screening and

Baseline visits (Visits 1, 2, 3). Medical history will be summarized using frequencies and percentages according to the SOC and PT.

## 7 Safety Analysis

The primary objective of the study is to investigate the safety, tolerability, and pharmacokinetics of treatment with NNZ-2591 in children and adolescents with PTHS.

All safety analyses will be based on the Safety Population.

Safety will be assessed based on incidence of treatment emergent adverse events (TEAEs), serious adverse events (SAEs), changes in vital signs, changes in laboratory measures, neurological, ophthalmological, and physical exam results, and changes in ECG's.

Tolerability will be assessed based on daily dosing logs, requiring dosing adjustments or discontinuations, dosing compliance, and AEs related to subject experience.

Pharmacokinetics will be summarized separately outside of this SAP.

